# 4.2. Intervention.

All procedures will be conducted as part of standard of care. In the Pharmacist Care group, each e-visit message requesting Paxlovid will be assigned to a pharmacist on the regional team. Pharmacists will review requests using a standard protocol. They will call patients via telephone to elicit additional information where needed, file Paxlovid prescriptions when appropriate, and arrange home delivery when requested.

The protocol for pharmacists has a list of common potential drug-drug interactions and provides guidance for how these should be handled. Drug-drug interactions are documented by pharmacists using a smartphrase in Epic, the electronic health record (EHR). Some DDIs may lead to changes in medications while a patient is taking Paxlovid.

In the AFM Pool Care group, each e-visit message requesting Paxlovid will be assigned to a pool of AFM physicians based at the medical centers in a given service area. Physicians will review requests using the existing standard regional protocol (as well as any existing medical center-level protocols). The regional Paxlovid E-visit User Guide illustrates how to use SmartSets to document the plan and respond to patients with the outcome (eligible, not eligible, or further discussion needed). Following this protocol, physicians call patients via telephone to elicit additional information where needed, file Paxlovid prescriptions when appropriate, and arrange home delivery when requested.

4.3. Randomization. In each of the participating service areas, facilities have been assigned at random to either the Pharmacist Care or AFM Pool Care group. We used covariate-constrained randomization, a method to prevent imbalances on important variables that may be associated with the outcomes. We conducted preliminary analyses to characterize facilities with regard to population size, socioeconomic status (using the Neighborhood Deprivation Index), race, ethnicity, and COVID-19 incidence in the service area since the start of the pandemic. We have chosen these variables for use in the restricted randomization given the expected association with study outcomes, along with the expected level of between facility variability which would increase the likelihood of between-arm imbalance. We also stratify randomization on service area for within-area balance on number of facilities assigned to the Pharmacist Care and AFM Care groups.

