#### 4.5. Data collection.

The primary outcome will be measured only among patients who have common potential drugdrug interactions (DDIs) based on a pre-specified list of medications. The outcome will be whether or not they received relevant counseling for any of their DDIs. Eligible patients in both groups will be selected using computerized pharmacy codes generated based on the protocol used by the regional pharmacy team. The computerized pharmacy codes will be used to identify patients with any of these potential DDIs in a consistent way in the Pharmacist Care and AFM Pool Care groups.

Research assistants blinded to group assignment will review text extracts from the EHR using a structured protocol to identify whether there is documentation that the patient received counseling regarding a DDI. With each study group, a random sample of eligible patients will be identified; the sample will be stratified by facility to yield a representative sample. Masking of group assignment will be conducted by one research assistant prior to review by a different

research assistant. A patient with any potential DDI will be counted as having received relevant counseling if any counseling (for any potential DDI) was documented in the text extra prior to or coincident with a Paxlovid prescription, or in the absence of a Paxlovid prescription, occurring within 2 days after the e-visit.

For the secondary outcomes, we will use data available from KPNC computerized sources, including HealthConnect (HC, aka EPIC) EHR data (from Clarity) and EPIC access logs. EHR data will be used to identify all e-visits for Paxlovid during the study period. For each patient who made an e-visit, the EPIC access log data for the subsequent 5-day period will be analyzed to identify how many minutes of pharmacist or physician time were associated with that request.

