Patient satisfaction and other care experience scores will be compared between the study groups using linear mixed effects regression with log transformation if needed for skewed data, with analyses paralleling that described for the other secondary outcomes.

For all aims, secondary analyses will assess variation in the estimates of treatment effect by age, race/ethnicity/language group, and comorbidity score group (high, medium, low) via stratification by level of the potential effect modifier. These stratified analyses will inform the fitting of regression models with appropriate cross-product terms between the potential effect modifier and study group indicator variable, allowing for a more formal assessment of heterogeneity in treatment effect.

A service area or facility may drop out before completion of the study if they were assigned to AFM Pool Care but add local pharmacist management, thus diverging from their assigned group. Paxlovid e-visits from such a service area or facility will be censored as of the dropout date (the date that local pharmacist management began).

Tests of significance will be two-tailed with an alpha of .05. No Bonferroni or other formal correction for multiple comparisons will be used, but results will be interpreted with the multiple testing issue in mind.

4.8. Sample size and power. To estimate the available sample, we extrapolated from April 2023. This was a month when COVID-19 incidence was low to medium; 4900 e-visits for Paxlovid were made across the 15 KPNC service areas. Based on this, an average of 1089 e-visits occur per week during low to medium COVID-19 incidence periods. However, e-visits that need to be answered on weekend days will not be eligible for pharmacist management; all of these will be excluded from the study. If 5 out of 7 e-visits occur on weekdays, an estimated 778 e-visits occur on weekdays during times of low to medium COVID-19 incidence.

This study will include 17 facilities that serve 872,200 adult members, or 25% of the 3.55 million adult members in the region. Each week, the estimated number of e-visits eligible for study is 25% of 778, or 195. Assuming an 8-week evaluation period, the estimated sample size is 1,560, or 92 patients in each of the 17 clusters.

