Given the group-randomization study design, calculation of sample sizes and minimum detectable treatment effects must account for the expected intraclass correlation (ICC) of observations within facilities. The ICCs in outcomes of interest are expected to be quite small, and therefore we present minimum detectable effects for an expected ICC of .01.

For Aim 1, the primary outcome is the % of patients with common potential DDIs who received counseling. We conservatively estimate that 70% of patients in the Pharmacist Care group will have received DDI counseling. A clinically meaningful difference between the two groups would be a relative risk (RR) of 0.8, which corresponds to a small effect size. To attain 80% power to identify such an effect with a two-tailed alpha of 0.05 and an ICC of .01, we need a sample size of 250 in each group and will plan our review of text extracts from the EHR accordingly.

For Aim 2, the example hypothesis is that the cost of management per e-visit for Paxlovid will be lower in the Pharmacist Care group than in the AFM Pool Care group. Given a two-tailed alpha of .05, the sample size of this study has 80% power to identify an effect size of 0.20 standard deviation units, which is a relatively small effect size. In other words, this study will have good power to find a statistically significant difference between the Pharmacist Care and AFM Pool Care groups even if the effect is relatively small.

For the patient survey in Aim 3, the sample size is selected to balance power and feasibility. We aim to collect completed surveys from 200 patients in each of the two study groups. We

estimate a response rate of 60%. To obtain 200 completed surveys in each group, we estimate needing to attempt surveys with 333 patients in each group. The completed sample size of 200 in each group will give us good power to identify relatively small differences in satisfaction scores, which are measured on a continuous scale. We will be able to detect effect sizes of .31 relative to a standard deviation of 1.

The purpose of the pharmacist and AFM surveys is process assessment and performance improvement. These surveys will focus on qualitative, open-ended responses; thus, sample size and power are not estimated here. We will survey all pharmacists on the regional team providing Paxlovid e-visits (estimated n=10). We also will survey the AFMs who are Paxlovid e-visit site leads (estimated n=12).

Date	Operational team	Research team

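### The power figures in 4.8 assume 17 equal facilities and normal quantiles; for the facility-assigned comparison, now secondary, they are mildly too favourable: about 74-77% on 15 df, lower if facility sizes differ

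*Combined protocol and SAP*

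**What the plan says.** Section 4.8 sizes all three aims on facility randomisation, with an expected ICC of .01. It takes the available sample as 17 clusters of one size: "the estimated sample size is 1,560, or 92 patients in each of the 17 clusters".

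- **Aim 1.** "We conservatively estimate that 70% of patients in the Pharmacist Care group will have received DDI counseling". The target is a relative risk of 0.8. The required number is 250 per group, "To attain 80% power to identify such an effect with a two-tailed alpha of 0.05 and an ICC of .01".
- **Aim 2.** "the sample size of this study has 80% power to identify an effect size of 0.20 standard deviation units".
- **Aim 3.** With 200 completed surveys per group, "We will be able to detect effect sizes of .31 relative to a standard deviation of 1".

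Section 4.6 sets the error rate: "Tests of significance will be two-tailed with an alpha of .05". It names mixed-effects logistic and linear models but no method for degrees of freedom. It makes the comparison by type of clinician who first opened the e-visit the primary analysis, and the comparison by assigned facility the secondary, intention-to-treat one.

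On facility size, 4.3 lists population size among the variables constraining the randomisation, chosen for their expected association with outcomes "along with the expected level of between facility variability which would increase the likelihood of between-arm imbalance". For the chart review, 4.5 says "the sample will be stratified by facility to yield a representative sample". Neither section gives the spread of facility sizes or the number of facilities per arm.

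**The concern.** A comparison between two sets of randomised facilities takes its error from variation between facilities. With 17 of them, the reference distribution has at most 17 - 2 = 15 df. Normal quantiles treat that variance as known and so overstate power at a true two-sided .05. If facilities also contribute unequal numbers, the same total carries less information than 17 equal clusters would.

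What is at stake is how null results are read. Section 4.8 promises good power even for relatively small effects, Aim 3 gives comparable satisfaction as its example hypothesis, and the abstract would support continuing pharmacist management if outcomes are better or similar. A non-significant facility-assigned difference would look more reassuring than it should if the detectable effects are understated.

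**Working it through.** **Inputs from the documents.** Two-sided alpha .05; 80% power; ICC .01; 17 facilities. Aim 1: 70% versus 0.8 × 70% = 56%, difference .14, 500 charts, 500/17 = 29.4 per facility. Aim 2: 1,560/17 = 91.8 per facility, effect 0.20 SD. Aim 3: 400/17 = 23.5 per facility, effect .31 SD.

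**Assumed here.** 8 versus 9 facilities; CV of facility size from 0 to .8.

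**Step 1: reproduce the plan.** The design effect is DE = 1 + (m - 1) × .01, giving 1.284, 1.908 and 1.225 for Aims 1, 2 and 3.

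- Aim 1: n = [1.960√(2 × .63 × .37) + 0.842√(.70 × .30 + .56 × .44)]² / .14² = 186 per group. Then 186 × 1.284 = 239, close to the stated 250.
- Aims 2 and 3: detectable effect = (1.960 + 0.842)√(4·DE/N) = 0.196 and 0.310, against the stated 0.20 and .31. With DE = 1 they would be 0.142 and 0.280, so the ICC was applied.

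Equal clusters and normal quantiles therefore reproduce all three figures.

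**Step 2: change only the reference distribution.** SE = √[(DE/m)(v₁/8 + v₂/9)], where v₁ = .210 and v₂ = .2464 for Aim 1, and both are 1 for Aims 2 and 3.

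| | SE | effect/SE | power, normal | power, t on 15 df |
|---|---|---|---|---|
| Aim 1 | .0484 | 2.893 | 82.5% | 77% |
| Aim 2 | .0701 | 2.855 | 81.5% | 76% |
| Aim 3 | .1109 | 2.796 | 79.8% | 74% |

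The t column is the noncentral t with critical value 2.131. The multiplier for 80% power rises from 2.802 to 2.998, so the detectable effects are 2.998 × .0701 = 0.210 SD and 2.998 × .1109 = .332 SD. An even split of the information between arms, in place of 8 versus 9, gives 77.1%, 76.2% and 74.5%, so that assumption matters little. Charging 3 more df for the four service-area strata (12 df) gives about 76%, 75% and 73%.

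**Step 3: add unequal size.** Each facility contributes information m/(1 + (m - 1) × .01), summed within arm; this is the efficient weighting of a mixed model. Sizes were drawn from a gamma distribution with the stated nominal CV, scaled to the fixed total, put 8 versus 9 at random, and results averaged over draws, with t on 15 df.

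| CV (assumed) | Aim 1 power | Aim 2 power at 0.20 SD | Aim 3 power at .31 SD | Aim 2 detectable | Aim 3 detectable |
|---|---|---|---|---|---|
| 0 | 77% | 76% | 74% | 0.210 | .332 |
| .4 | 76% | 74% | 73% | 0.214 | .337 |
| .6 | 74% | 72% | 72% | 0.219 | .343 |
| .8 | 72% | 70% | 70% | 0.226 | .351 |

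Holding the information equal between arms gives about 73%, 70% and 71% at CV .8. The cruder design effect 1 + ((1 + CV²)m - 1) × ICC, which forgoes efficient weighting, takes Aim 2 down to 65% at CV .8.

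**Step 4: separate the two causes.** Unequal size alone, with normal quantiles at CV .6, leaves about 80%, 78% and 77%. The reference distribution alone takes off about 5 points in each aim.

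**The case against.** Several objections have force.

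- **The printed figures are right on their own assumptions.** This stands. It is not an arithmetic slip; the assumptions are favourable to the design.
- **The plan does not commit to a t reference.** True: 4.6 names no df method, and a normal-based mixed model would keep nominal power near 80%. But with 17 clusters that risks a type I error above the .05 that 4.6 sets, so it does not restore the claimed property.
- **The average of 92 need not mean equal facilities.** A reader might infer that the plan contradicts itself on facility size. It does not go that far. The remark in 4.3 on variability covers several variables, and 4.5 does not give the allocation of charts. Unequal samples are likely but inferred.
- **The facility-assigned comparison is no longer primary.** This stands and limits the point. Under the clinician-based grouping, exposure can vary within a facility, so neither 15 df nor this design effect describes it.
- **The ICC matters more.** Also true. At CV .6 on 15 df, Aim 2 power at 0.20 SD is about 84% at ICC .005 and 56% at ICC .02. The restated figures remain conditional on .01.
- **Nothing in the design can now change.** The enrolment window has closed, and 4.6 already promises interval estimates, which should carry the interpretation. This is why the point is minor.

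**Conclusion.** The point holds as a modest overstatement. For the facility-assigned analysis at ICC .01 and a true two-sided .05, the stated 80% is about 77%, 76% and 74% for Aims 1, 2 and 3 even with equal facilities, given at most 15 df and an assumed 8 versus 9 split. It falls to about 70-72% at an assumed CV of .8. Detectable effects are about 0.21-0.23 SD against 0.20, and .33-.35 SD against .31.

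Two stronger readings are tempting and not supported. One is a single corrected power such as 72-75%: that needs a facility-size CV which the documents do not give, and one range does not fit all three aims. The other is that the stated primary analysis is underpowered by this amount: these figures do not describe that analysis. They also leave out the crossover that 4.6 calls possible, which would dilute the facility-assigned effect.

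**What to change.** In 4.8, replace the equal allocation with the actual number of patients per facility, or their mean and CV, from counts the sponsor already holds. Recompute using the sum of m/(1 + (m - 1) × ICC) within each arm and a t reference on the between-facility df. Restate the Aim 1 power and the Aim 2 and Aim 3 detectable effects from that calculation; the figures above only indicate what to expect.

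In 4.6, specify the same small-sample degrees of freedom for the facility-assigned mixed models.

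State in 4.8 that the figures apply to the facility-assigned analysis, not to the primary analysis by clinician who first accessed the e-visit, and that they make no allowance for crossover.

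The cost is a recalculation and slightly less favourable figures. No more patients or charts are needed.

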## 4.9 Timeline

## 4. Projected Impact

This study's findings quality of care, cost, and patient and clinician satisfaction will inform decisions about how to deploy pharmacist effort for KPNC. The study leaders include regional leaders for Virtual Medicine and Pharmacy who are well-positioned to make implementation decisions based on the results we generate.

## 5. Deliverables and Dissemination Plan

Our deliverables and dissemination plan have two purposes: To provide information for operational decisions by TPMG and KFH, and to establish our reputation as leaders in Desktop Medicine and Pharmacy Services through publication. Specific deliverables and plans include:

- The PI will prepare a presentation prior to study initiation to support conversations with leaders of service areas that will be included.
- Soon after the analysis of computerized data is completed, we will create an internal report for Drs. [name] and [name] to share via presentation to the appropriate chiefs and other operational leadership groups.
- The analysis of clinician and patient data will be completed after this, and we will update the internal report to support a follow-up communication.
- We will write a manuscript for submission to a peer-reviewed journal to share our findings with health care leaders in the U.S. and beyond.

